Antibody Mediated Rejection	
Antibody Mediated Rejection (AMR) will be defined based on the Revision of the 1996 Working Formulation for the Standardization of Nomenclature in the Diagnosis of Lung Rejection and the Pathology of pulmonary antibody mediated rejection and the 2012 update from the Pathology Council of the ISHLT.^{103,104} AMR will be diagnosed based on the presence of one or more of the following:
 
 • Donor Specific Antibody (DSA) or autoantibody; • Abnormal Histology; • Graft Dysfunction.
Anonymized	
A sample that was previously identifiable, has had all identifiers removed and can no longer be linked back to the subject or the subject's medical record by any means.

Chronic Allograft Dysfunction	
Chronic allograft dysfunction will be diagnosed locally based on ISHLT criteria for BOS or histologic evidence of obliterans bronchiolitis.^{103, 105} Local sites will rule out acute rejection, acute infection and airway stenosis or narrowing prior to diagnosing chronic allograft dysfunction.

Donor Specific Antibodies or Autoantibodies	
Circulating antibody to HLA or other antigens expressed on donor endothelial cells.

Inadequate Weight Gain	
Drop between 5-10 percentile points

Infectious Events	
Infectious events will be defined using published criteria from the ISHLT.¹⁰⁶ The 2010 guidelines on defining infections in cardiothoracic transplantation provide classification of bacterial, fungal and viral pulmonary infections in lung transplant recipients.

Lost to Follow-Up	
The CTOTC-08 subject may be considered "lost to follow up" after the subject misses a minimum of 3 consecutive study visits, and the site personnel has made a number of unsuccessful phone contacts. The decision to early terminate the subject will be the decision of the site PI, all attempts to establish contact with the subject will be documented in the study files.

Tacrolimus Variability Intervention	A series of calls with the participant, parent(s)/guardian(s) and specifically trained call center personnel to address barriers to adherence, using a manualized intervention.
Tacrolimus Variability Threshold	SD of 2.0 or more (outpatient tacrolimus trough levels) or an undetectable tacrolimus trough level.
Primary Graft Dysfunction	PGD is defined according to the recent summary statement from the ISHLT and will be graded from 0 to 3 based on radiographic changes and the ratio of PaO ₂ /FiO ₂ . ¹⁰⁷

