7.5.2. Antibody Mediated Rejection

Antibody Medicated Rejection (AMR) will be graded locally as shown in **Table 5**.

	DSA ¹ or Autoantibody	Abnormal Histology ²	Graft Dysfunction ³
I: Latent humoral response	X		
II: Subclinical humoral rejection	X	X	
III: Humoral rejection	X	X	X

¹ Circulating antibody to HLA or other antigens expressed in lung tissue.

² Including neutrophilic capillaritis or septal margination, high grade ($\geq A3$) or persistent / recurrent acute rejection, acute lung injury/diffuse alveolar damage, high grade (B2R) or persistent low grade (B1R) lymphocytic bronchitis, obliterative bronchiolitis, arteritis in the absence of acute rejection or other finding not explained by clinical circumstances (i.e. infectious causes thoroughly excluded)

³ Unexplained (i.e. infectious causes thoroughly excluded) persistent (> 1 week) change in respiratory status manifested by two MAJOR OR one MAJOR plus one or more MINOR criteria listed below:

MAJOR CRITERIA:

- I. Increase in resting respiratory rate $\geq 10\%$
- II. Decrease in resting SaO₂ $\geq 4\%$
- III. Persistent drop in FEV1 of $\geq 10\%$

MINOR CRITERIA:

- I. Daily repetitive cough
- II. Auscultatory findings
- III. Inadequate weight gain defined as a drop between 5-10 percentile points
- IV. CXR or CT changes

Table 5: Antibody Mediated Rejection Diagnostic Grading

Study participants will be screened for donor specific antibodies (DSA) monthly for the first 3 months following transplantation and then every 3 months if negative. C4d immunohistochemistry will be performed on all TBBx. AMR will be treated as described below.

I: Latent humoral response	No treatment, consider monitoring DSA more frequently
II: Subclinical humoral rejection	
 1. Administer methylprednisolone 10-20 mg/kg/day (max = 1 g/day) for 3 to 4 days AND return to maintenance steroid dosing. 2. Follow-up TBBx performed 2-4 weeks following completion of therapy. The local investigator may consider open lung biopsy if graft dysfunction is present. 3. If subclinical humoral rejection persists on the follow up biopsy, plasmapheresis will be performed.

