7.3.1. Post-transplant Clinical Endpoints

Variable: Secondary incidence endpoints including:

- Chronic allograft dysfunction, defined as indicated for the primary endpoint
- Listing for re-transplant, defined as indicated for the primary endpoint
- Death, defined as indicated for the primary endpoint
- Primary Graft Dysfunction (PGD), defined at 0, 24, 48, and 72 hours post-transplant per Section 7.5.4 of the protocol
- Grade A Acute Rejection, reported locally as defined in Section 7.5.1 of the protocol

- Antibody Mediated Rejection of Grade II or III, reported locally as defined in Section 7.5.2 of the protocol
 - Additionally, if the data allow, AMR will be evaluated according to the 2016 ISHLT consensus guidelines published in the Journal of Heart and Lung Transplantation.

Analysis: For each of the above incidence endpoints, the proportion of subjects with events will be reported by treatment group with a corresponding 90% confidence interval, and for PGD and the rejection endpoints the treatment groups will be compared using a Chi-square or Fisher's Exact test. The incidence of grade 2 or higher PGD will be summarized overall and at each of the 4 time points separately. Additionally, for acute rejection and antibody mediated rejection, number of events per person time (e.g., year) will be estimated.

An example of SAS code to be used:

```
Proc freq;  
  tables treatment_group * endpoint / chisq measures cl alpha=0.1;  
run;
```

Variable: Incidence of meeting the tacrolimus variability threshold

Analysis: Among subjects who have at least 3 outpatient tacrolimus trough levels collected that are at least 3 months (i.e., greater than or equal to 3 months) post-transplant, an estimate of the standard deviation of tacrolimus levels will be produced for each subject. This estimate will be a rolling estimate (continually re-assessed) and may use up to 1 year worth of trough levels at any given time. The proportion of subjects with an estimated standard deviation at any time of 2.0 ng/mL or greater will be reported with a corresponding 90% confidence interval.

Variable: Incidence of completion of the Tacrolimus Variability Intervention (TVI)

Analysis: Among subjects who qualified for and agreed to participate in the TVI, the proportion of subjects who complete the intervention will be reported with a corresponding 90% confidence interval.

Variable: Magnitude of change in standard deviation of tacrolimus levels following intervention

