We will analyze DSA and each type of antibody separately. The DSA and autoantibody data will consist of binary (positive/negative) or ordinal (negative/weak positive/strong positive) responses measured repeatedly at scheduled and unequally spaced intervals. With these features of the data and at this sample size, it may not be feasible to obtain estimates of treatment effect at each time-point using a single statistical model with rituximab and time main effects and their interaction as covariates. Therefore, we will describe the treatment effect over the course of the follow-up period.

The hazard ratio for the association between development of antibodies and clinical outcomes (the endpoint and its components, and the secondary incidence endpoints) will be estimated with its 90% confidence interval using a Cox proportional hazard model with presence or absence of antibodies as time-dependent repeated measures covariates, stratified by treatment group. We will model the association of each antibody on each outcome separately and in combination.

As permitted by the data, we will estimate odds ratios with 90% confidence intervals for the associations between each of the various serum antibodies and C4d staining of the graft tissue. We will estimate these odds ratios at each time point between each pair of antibodies and each antibody and C4d result, both cross-sectional, and cumulative, in which case we would treat any subject with a current or prior positive result as positive for that particular antibody.

Immunophenotyping of B cell and T cell subsets from flow cytometry will be examined. B cell and T cell fractions will be compared between treatment groups within a repeated measures mixed model framework while utilizing samples from the pre-transplant, weeks 4-6, and months

3, 6, 12 and 18 time points. P-values from Tukey's HSD test will be reported to account for multiple comparisons of the mean cell fractions between groups at the various time points.

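### The antibody hazard ratio for AMR is circular because grades II and III require an antibody, and for PGD antibody arising after transplant has almost no exposed time at risk

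*SAP*

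**What the plan says.** SAP 7.4 sets out "The hazard ratio for the association between development of antibodies and clinical outcomes", naming the outcomes as "the endpoint and its components, and the secondary incidence endpoints". The model is a Cox regression with "presence or absence of antibodies as time-dependent repeated measures covariates, stratified by treatment group", reported with a 90% confidence interval. It adds: "We will model the association of each antibody on each outcome separately and in combination". Protocol 13.4.5 contains the same plan under its exploratory endpoints.

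SAP 7.3.1 lists the secondary incidence endpoints. Two matter here:

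- "Antibody Mediated Rejection of Grade II or III, reported locally as defined in Section 7.5.2 of the protocol"
- "Primary Graft Dysfunction (PGD), defined at 0, 24, 48, and 72 hours post-transplant per Section 7.5.4 of the protocol"

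In the grading table of protocol 7.5.2, the column for DSA or autoantibody is marked for grades I, II and III. A footnote describes the criterion as "Circulating antibody to HLA or other antigens expressed in lung tissue". The protocol's Study Definitions Page reads differently: "AMR will be diagnosed based on the presence of one or more of the following", followed by antibody, abnormal histology and graft dysfunction.

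**The concern.** A hazard ratio for antibody and outcome is informative only if the outcome can occur with or without the antibody. Under protocol 7.5.2, AMR of grade II or III cannot. A Cox model of AMR on antibody status therefore partly measures the grading rule and not biology.

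For PGD the difficulty is time order. The exposure is described as antibody development, but the outcome is settled by 72 hours, before nearly all post-transplant antibody samples are drawn.

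The protocol's hypothesis (section 1.1) is that rituximab improves outcomes partly by reducing these antibodies. A raised antibody-AMR hazard ratio could be taken as support for that mechanism when the definition alone would produce it.

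**Working it through.** The documents give no value for these hazard ratios, so there is no planned figure to reproduce.

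**AMR: inputs**
- Pre-transplant autoantibodies: collagen V 33%, K-alpha-1 tubulin 44% (protocol 2.4, earlier pediatric cohort).
- DSA: 3% class I before transplant in that cohort; 56% after transplant in the adult series (protocol 2.4). These serve as low and high values.
- Assumptions: antibody has no causal effect; the same assay result feeds both grading and covariate; each antibody is independent of the others taken together.

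**AMR: formula.** Let qualifying histology (with or without graft dysfunction) arise at rate h regardless of antibody. AMR then has hazard h while any qualifying antibody is present and 0 otherwise.
- Any-antibody indicator: HR = h/0, infinite.
- One antibody alone: HR = h/(q·h) = 1/q, where q is the share of subjects negative for that antibody who carry another qualifying one.

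The smallest q is the prevalence of the commoner of the other two antibodies (complete overlap). The largest is their sum (no overlap).

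| Antibody modelled | Other antibodies | q, range | HR = 1/q | q and HR if the others are independent |
|---|---|---|---|---|
| DSA | 33%, 44% | 0.44 to 0.77 | 1.30-2.27 | 1 − 0.67×0.56 = 0.625; 1.60 |
| K-alpha-1 tubulin | 33%, DSA 3% | 0.33 to 0.36 | 2.78-3.03 | 1 − 0.67×0.97 = 0.350; 2.86 |
| Collagen V | 44%, DSA 3% | 0.44 to 0.47 | 2.13-2.27 | 1 − 0.56×0.97 = 0.457; 2.19 |
| K-alpha-1 tubulin | 33%, DSA 56% | 0.56 to 0.89 | 1.12-1.79 | 1 − 0.67×0.44 = 0.705; 1.42 |
| Collagen V | 44%, DSA 56% | 0.56 to 1.00 | 1.00-1.79 | 1 − 0.56×0.44 = 0.754; 1.33 |

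**AMR: simulation.** Time-dependent Cox models were fitted to data with no causal effect, not stratified by arm. Assumed: pre-transplant prevalences as above, 53% later DSA, 20% later conversion for each autoantibody, and an AMR hazard of 0.03 per month while antibody-positive. Median hazard ratios for DSA, collagen V and K-alpha-1 tubulin were 1.37, 1.44 and 1.50 with 50 subjects, and 1.50, 1.34 and 1.59 with 2000. Events in time free of all three antibodies were 0 of 8298 and 0 of 5465. Those zeros are built into the simulation, as they are into the grading rule.

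**PGD: timing**
- Outcome: graded at 0, 24, 48 and 72 hours (SAP 7.3.1).
- Antibody samples (protocol Appendix 1 and its notes): Visit 00, up to 60 days before transplant; Visit 01, up to 72 hours after; Visit 02, 1-2 weeks after.

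Visit 01 is the only post-transplant sample that can precede a PGD grade, and it may be drawn as late as the last grade. A change from negative to positive after transplant therefore contributes almost no exposed time before PGD is decided. Pre-transplant status does precede it. A null Cox model with 44% antibody-positive and an assumed PGD rate of 30% gave a median hazard ratio of 0.98, so that analysis shows no built-in bias.

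**The case against.** The strongest objection is that a reader might infer that both results are artefacts and that the AMR hazard ratio must be infinite. The documents support neither.

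- **PGD.** A correctly ordered time-dependent covariate starts from pre-transplant status, which is a legitimate exposure. An artefact would arise only if antibody found after PGD were counted as exposure, and the SAP does not say that it will be. This stands: the fault is lack of exposed time.
- **AMR size.** SAP 7.4 analyses each antibody separately as well as in combination. Since any one qualifying antibody satisfies the criterion, AMR can occur in time negative for the antibody modelled. Combination could also mean several antibodies entered jointly, which need not give infinite coefficients. Further, AMR is graded locally while protocol 9.1 assigns the antibody assays to a core laboratory, and the criterion admits antibodies outside the modelled set. Any of these can make the estimate finite. All this stands on size, but none of it removes the antibody requirement from the outcome.
- **Other AMR definitions.** Under the Study Definitions Page, antibody is not required. The SAP cites 7.5.2 instead, so the circularity applies as planned. SAP 7.3.1 also foresees AMR by 2016 ISHLT guidelines if data allow; these documents do not show whether antibody is required there.
- **Importance.** SAP 7.4 ties its test of autoantibodies as predictors of injury to the primary endpoint, and tests rituximab's effect on antibodies by comparing titers between arms. Neither depends on the AMR or PGD hazard ratios. This stands and limits the consequence.

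**Conclusion.** The point holds for AMR as circularity and for PGD as a limit on what can be estimated.

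For AMR grade II or III as the SAP defines it, the any-antibody hazard ratio is infinite under no effect if assays agree. If local and core results disagree it is finite but still driven by the definition. Single-antibody hazard ratios are biased upward, by a factor of about 1.0-3.0 under no effect. That range rests on the prevalences quoted in protocol 2.4, one of them from adults, and on the independence and concordance assumptions above.

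For PGD, a hazard ratio for newly developing antibody is essentially not estimable; one for pre-transplant antibody is valid.

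These are mechanistic analyses, and the randomized comparison on the primary endpoint is untouched.

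**What to change.** Amend SAP 7.4, noting that protocol 13.4.5 carries the same wording:

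1. Remove AMR from the antibody Cox models. Report antibody status among AMR cases descriptively. If an antibody-free outcome is wanted, use biopsy histology where it is already recorded; protocol 8.4 has local biopsy readings entered on case report forms.
2. For PGD, use only pre-transplant antibody as the exposure.
3. Keep chronic allograft dysfunction, relisting, death and grade A rejection as outcomes.
4. Reconcile the AMR definition on the protocol's Study Definitions Page with section 7.5.2, and state which one the analysis uses.

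The cost is wording and the loss of one exploratory association. Rescoring the graft-dysfunction part of AMR without regard to antibody is not shown to be free of new data. Its major criteria are resting respiratory rate, oxygen saturation and FEV1. The physical examination row in Appendix 1 lists neither of the first two, and pulmonary function tests are collected only when done as standard of care.

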The hazard ratio for the association between development of antibodies and clinical outcomes (the endpoint and its components, and the secondary incidence endpoints) will be estimated with its 90% confidence interval using a Cox proportional hazard model with presence or absence of antibodies as time-dependent repeated measures covariates, stratified by treatment group. We will model the association of each antibody on each outcome separately and in combination.

We will also estimate odds ratios with 90% confidence intervals for the associations between each of the various serum antibodies and C4d staining of the graft tissue. We will estimate these odds ratios at each time point between each pair of antibodies and each antibody and C4d result, both cross-sectional, and cumulative, in which case we would treat any subject with a current or prior positive result as positive for that particular antibody.

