1. PROTOCOL SYNOPSIS

Title	B cell Targeted Induction to Improve Outcomes in Pediatric Lung Transplantation
Clinical Phase	Phase 2
Number of Sites	7 US Sites
IND Sponsor/Number	NIAID/IND Number 121403
Primary Study Objective	To determine whether rituximab induction along with standard of care immunosuppression will improve outcomes following pediatric lung transplantation.
Secondary Study Objectives	
 1. To determine the effects of rituximab induction on post-transplant immunity in pediatric lung transplant recipients. 2. To assess the safety and tolerability of rituximab. 3. To assess the feasibility of a phone based intervention to decrease tacrolimus trough level variability.
Study Design/Treatment Description	Phase 2, prospective, multi-center, double-blind, randomized, placebo-controlled clinical trial in which 50 primary pediatric lung transplant recipients will be randomized (1:1) to receive either induction therapy with anti-CD20 mAb (375 mg/m ²) IV or placebo (IV day 0 and day 12 post-transplant) plus standard of care immunosuppression (thymoglobulin induction, tacrolimus or generic equivalent, MMF or generic equivalent, and steroids).
Primary Endpoint	
The primary endpoint is a composite of the earliest time to any of the following events during the follow-up period:
 
 • Chronic Allograft Dysfunction • Listed for Retransplant • Death
Secondary Clinical Endpoints	
 1. Post-transplant clinical outcomes including: 
 a. Incidence of chronic allograft dysfunction, listing for retransplantation, and death during the follow-up period, which will be a minimum of 12 months post-transplant b. Incidence of Primary Graft Dysfunction c. Incidence of Grade A Acute Rejection during the follow-up period, which will be a minimum of 12 months post-transplant d. Incidence of Antibody Mediated Rejection during the follow-up period, which will be a minimum of 12 months post-transplant e. Incidence of tacrolimus variability threshold during the follow-up period, which will be a minimum of 12 months f. Percentage of participants meeting tacrolimus variability threshold who complete tacrolimus variability intervention

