	
 g. Magnitude of change in standard deviation of tacrolimus levels following intervention 
2. Post-transplant safety outcomes including:
 
 a. Incidence and severity of infection episodes b. Serious adverse events related to rituximab
Secondary Mechanistic Endpoints	
 1. Incidence and kinetics of DSA and autoantibodies, specifically Collagen V (ColV) and k-alpha-1 tubulin (kα1T) 2. Frequency, kinetics, phenotype and function of peripheral B cells 3. Frequency, kinetics and cytokine profiles of allo- and auto reactive T cells 4. Incidence and quantity of B cells and B cell proximity to other cells in the graft tissue
Accrual Objective	50 randomized pediatric lung transplant recipients
Study Duration	
4.5 years (3.5 year accrual + 1-4.5 year follow-up period)
 
All participants will be followed for a minimum of 1 year post-transplant. Participants will continue follow-up visits (up to 4.5 years post-transplant) until the last participant completes 1 year of follow-up.

Enrollment Inclusion Criteria	
 1. Subject and/or parent/guardian must be able to understand and provide informed consent 2. Less than or equal to 21 years of age 3. Candidate for primary lung transplant (listed for lung transplant) 4. Female and male subjects with reproductive potential must agree to use FDA approved methods of birth control for 12 months after completion of treatment 5. Adequate bone marrow function based on the following criteria: 
 a. ANC > 1000mm³ b. Platelets > 100,000/mm³ c. Hemoglobin > 7 g/dL d. AST or ALT <2x Upper Limit of Normal unless related to primary disease
Enrollment Exclusion Criteria	
 1. Inability or unwillingness of a participant to give written informed consent or comply with study protocol 2. Multi-organ transplant 3. Previous treatment with rituximab (Rituxan®) 4. History of severe allergic anaphylactic reactions to humanized or murine monoclonal antibodies 5. History of severe reaction to previous therapy with IVIG 6. History of Burkholderia cenocepacia 7. History of anti-CD20 therapy

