7.4. Secondary Mechanistic Endpoints

The following mechanistic endpoints will be assessed using the ITT sample:

- Incidence and kinetics of DSA and autoantibodies, specifically Collagen V (CoIV) and κ 1T
- Frequency, kinetics, phenotype and function of peripheral B cells
- Frequency, kinetics and cytokine profiles of allo and auto-reactive T cells
- Incidence and quantity of B cells and B cell proximity to other cells in the graft tissue

We will correlate pre and/or post-transplant serum reactivity to each autoantigen and to donor HLA with our primary endpoint to prospectively and independently test the hypothesis that autoantibodies can be used as predictors of incipient injury. We will also correlate the presence of serum antibodies with positive C4d staining of the graft tissue (to be collected as part of the clinical component of the study).

To test the hypothesis that rituximab prevents induction of de novo autoantibodies and or DSA, we will compare titers of autoantibodies (or DSA) between the rituximab and control groups. Development of antibodies to either DSA or self-antigens or both and the kinetics of antibody development (time course following transplantation) will be correlated with clinical evidence of AMR and BOS as determined in the clinical part of study described above and the ISHLT criterion. While the absolute numbers of patients in each group with preexisting autoantibodies or DSA is anticipated to be small (thus limiting power) we will compare and report pre vs post-transplant titers in each case to determine if rituximab impacts preexisting antibody.

The results will be analyzed for development of PGD, development of DSA, diagnosis of AMR and BOS. In addition we will also determine any correlation which may exist between the strength of antibodies detected for DSA, HLA and each antibody to self-antigens either alone or cumulatively and clinical outcomes such as PGD, AMR and BOS.

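### The antibody-antibody and antibody-C4d odds ratios are not stratified by arm, so they are biased above 1 after transplant if rituximab lowers both markers

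*SAP*

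**What the plan says.** SAP 7.4 sets the sample for the mechanistic work: "The following mechanistic endpoints will be assessed using the ITT sample". That sample holds both arms. The synopsis gives the target as "50 randomized pediatric lung transplant recipients" and the allocation as "recipients will be randomized (1:1) to receive", so there are at most 25 + 25.

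Within SAP 7.4, the Cox models that relate antibodies to clinical outcomes use antibody status as "time-dependent repeated measures covariates, stratified by treatment group". The next paragraph turns to association between markers. As the data permit, it will "estimate odds ratios with 90% confidence intervals for the associations" of each serum antibody with C4d, and then: "We will estimate these odds ratios at each time point between each pair of antibodies and each antibody and C4d result". Both a cross-sectional and a cumulative version are planned; in the cumulative version "we would treat any subject with a current or prior positive result as positive for that particular antibody". No stratum, covariate or by-arm presentation is named, and no test or p-value is attached.

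Protocol 13.4.5 has the same structure: a Cox model stratified by arm, followed by "We will also estimate odds ratios with 90% confidence intervals for the associations between each of the various serum antibodies and C4d staining" with no mention of arm.

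**The concern.** The aim is to learn whether antibodies occur together and whether they go with C4d in the graft. Treatment arm can be a common cause of both. Protocol 1.1 hypothesises that rituximab reduces donor-specific antibodies and antibodies to lung self-antigens, and C4d could fall with them. If two markers fall independently, subjects negative for both gather in the rituximab arm and subjects positive for both gather in the placebo arm. An odds ratio taken over the combined sample then shows a positive association that only restates the treatment effect.

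At stake is the reading of the mechanistic results. A crude odds ratio above 1 could be taken as evidence that antibodies track one another or track graft C4d when neither holds within an arm. The primary, secondary clinical and safety analyses are not affected.

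**Working it through.** The plan gives no expected value, power or sample size for these odds ratios, so there is no figure to reproduce. The check asks what the unstratified odds ratio estimates when the true within-arm odds ratio is 1.

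**Inputs**

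- 25 per arm (SAP synopsis) and two-sided 90% intervals (SAP 7.4).
- Control-arm antibody rates by proxy from Protocol 2.4: 56% (donor-specific antibody, 65 of 116 adult recipients), and 44% and 33% (antibodies to k-alpha-1 tubulin and collagen V in children before transplant).
- Control-arm C4d rate: not in the documents; 30% and 15% assumed.
- Effect of rituximab on marker rates: not in the documents; cuts of 25%, 50% and 75% assumed.

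**Direction**

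Let the two markers have rates p and q on placebo and p′ and q′ on rituximab, independent within arm, with equal arms. In the combined sample,

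P(both positive) − P(first positive) × P(second positive) = (p − p′)(q − q′)/4.

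This is positive when both markers fall and zero when only one moves. It is also zero before transplant, where treatment cannot have changed either rate.

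**Size, worked for 56%/44% halved to 28%/22%**

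- Both positive: (0.56×0.44 + 0.28×0.22)/2 = 0.154
- First only: (0.56×0.56 + 0.28×0.78)/2 = 0.266
- Second only: (0.44×0.44 + 0.72×0.22)/2 = 0.176
- Neither: (0.44×0.56 + 0.72×0.78)/2 = 0.404
- Odds ratio: (0.154×0.404)/(0.266×0.176) = 1.33

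With a 75% cut (14%/11%) the four cells are 0.1309, 0.2191, 0.1441 and 0.5059, giving an odds ratio of 2.10.

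**How often the 90% interval excludes 1**

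This comes from 200,000 simulated trials per row. Crude is a Wald interval. Stratified is Mantel-Haenszel with the Robins-Breslow-Greenland variance. Trials with no finite estimate count as not excluding 1.

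| Control rates | Change on rituximab | Crude odds ratio | Crude excludes 1 | Stratified excludes 1 |
|---|---|---|---|---|
| 56%/44% | none | 1.00 | 10.2% | 9.8% |
| 56%/44% | first marker only, halved | 1.00 | 10.1% | 9.5% |
| 56%/44% | both cut 25% | 1.07 | 10.4% | 9.8% |
| 56%/44% | both halved | 1.33 | 13.7% | 9.5% |
| 44%/33% | both halved | 1.24 | 10.9% | 8.6% |
| 56%/30% (C4d assumed) | both halved | 1.28 | 10.7% | 8.7% |
| 56%/15% (C4d assumed) | both halved | 1.24 | 4.7% | 4.0% |
| 56%/44% | both cut 75% | 2.10 | 31.3% | 9.6% |
| 56%/30% (C4d assumed) | both cut 75% | 1.92 | 21.5% | 8.2% |
| 44%/33% | both cut 75% | 1.80 | 20.4% | 8.1% |

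The error is one-sided. At 56%/44% halved, the crude interval lies wholly above 1 in 12.1% of trials against a nominal 5%; stratified, the figure is 5.0%. The stratified odds ratio targets 1 in every row. In the 56%/15% row it could be estimated in 89% of trials.

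**The case against.** Four points can be made for leaving the text alone.

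First, a reader might infer that the plan states that the arms are combined. It does not; it is silent on arm. That stands as a matter of wording. But an odds ratio on a two-arm sample with no stratum named is a crude odds ratio if followed as written, and the neighbouring Cox model shows that stratification was named where it was wanted.

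Second, a reader might infer that the analysis would produce a statistically significant false association. The documents plan only estimates with 90% intervals here, with no test. This stands. The fair description is a biased estimate whose interval excludes 1 too often when the effects on both markers are large.

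Third, a reader might expect a large bias because Protocol 13.6 plans for large effects. Those hazard ratios, 0.40 and 0.33, concern the clinical composite; nothing in the documents plans an effect on marker prevalence. Falls from 60% to 20% in both markers would give an odds ratio of (0.20×0.40)/(0.20×0.20) = 2.0 and exclusion of 1 in 33% of trials, but those rates have no source in the documents. The nearest data, in Protocol 2.4, are adults given rituximab-based desensitization, of whom 46.7% and 48.4% lost their autoantibodies, which is roughly a halving. They describe treatment of existing antibody rather than induction, so they are only a proxy, but they point to the modest rows of the table.

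Fourth, Protocol 2.2 expects B cells to return over 3 to 6 months, which should shrink the bias at later visits. That holds for the cross-sectional version. The cumulative version carries an early difference between arms forward.

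**Conclusion.** The point holds in a limited form. Followed as written, the unstratified post-transplant odds ratios are biased above 1 whenever rituximab lowers both markers, even with no association within either arm. With 25 per arm, the bias is modest if both markers are halved (about 1.2 to 1.3, exclusion of 1 in about 5% to 14% of trials against a nominal 10%) and material if both fall by about 75% (about 1.8 to 2.1, 20% to 31%). It is absent before transplant and when only one marker changes.

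The direction follows from the algebra. The size rests on assumed effects of rituximab on the markers, assumed C4d rates, and antibody rates borrowed from adults and from children before transplant. The documents do not support a claim that a false association is the expected result. Because this is a mechanistic analysis, placed under exploratory endpoints in the protocol, the matter is of low severity, but the remedy is cheap.

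**What to change.** In SAP 7.4 and Protocol 13.4.5, state that each post-transplant odds ratio, antibody with antibody and antibody with C4d, is estimated stratified by treatment group with its 90% confidence interval. Use the Mantel-Haenszel common odds ratio, or exact conditional methods when cells are sparse. Apply this to both the cross-sectional and the cumulative versions. It brings these analyses into line with the Cox models beside them. In SAS it needs a three-way table with the CMH option in the PROC FREQ step that SAP 7.3.1 already uses.

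The cost is slightly wider intervals, and some odds ratios that cannot be estimated when a marker is rare: about 10% of trials at 56%/15% halved (100% − 89% = 11% in the run above), and more with fewer subjects at later visits. The SAP should say that such cases are reported as not estimable, with the counts shown by arm.
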